1.0 Study Summary

Study Title	Effects of Post-Exercise Recovery Drink Composition on Subsequent Performance in Masters Class Athletes
Study Design	Randomized, Double-blind, placebo-controlled between-subject
Primary Objective	The purpose of this study is to demonstrate that performance in a subsequent bout of high-intensity glycogen depleting exercise will not be significantly different regardless of post-exercise recovery drink (carbohydrate vs. carbohydrate and protein vs. placebo).
Secondary Objective(s)	Assess the level of sports nutrition knowledge and total daily carbohydrate and protein intake in a group of endurance-trained masters class athletes.
Research Intervention(s)/ Investigational Agent(s)	[name], MS, RDN [name] [name] [name] [name], BS
IND/IDE #	
Study Population	Male Athletes, Age 35-59 years
Sample Size	50
Study Duration for individual participants	14 days; 3-4 total visits
Study Specific Abbreviations/ Definitions	Graded Exercise Test (GXT), Maximal Oxygen Consumption (VO ₂ max), Plateau in Oxygen Uptake (VO ₂ peak), High-Intensity Aerobic Interval Exercise (INT), Time to Exhaustion (TTE), Heart Rate Variability (HRV), Sweat Rate (SR), Carbohydrate (CHO), Carbohydrate-Protein (CHO-P), Placebo (PLA), Masters Class Athletes (MCA's)

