2.0 Objectives*

- 2.1 The purpose of this investigation is to examine the effects of carbohydrate vs. carbohydrate-protein co-ingestion vs. placebo on a subsequent bout of performance following high-intensity exercise and a 2-hour recovery period in Masters Class Athletes.
- 2.2 It is hypothesized that:
 - Carbohydrate will improve subsequent performance significantly better than the placebo post-exercise in male Masters Class Athletes.
 - Carbohydrate and protein will improve subsequent performance significantly better than PLA post-exercise in male Masters Class Athletes.
 - Carbohydrate and Protein will not improve subsequent performance significantly better than CHO post-exercise in male Masters Class Athletes.

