4.0 Study Endpoints*

- 4.1 The study will be completed when participants have finished all visits to the laboratory. It is anticipated that the total testing for each individual should be completed within 14 days or 3-4 total visits.

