5.0 Study Intervention/Investigational Agent

- 1.1 Participants will consume either a CHO beverage (1.2 g/kg of bw), a CHO-P beverage (0.8 g/kg bw CHO + 0.4 g/kg bw protein), or PLA beverage matched for taste and appearance between exercise bouts to elucidate which drink moderates

performance decrements most effectively. The dietary source of CHO will be Gatorade®, the PLA will be Gatorade® G Zero, and the protein will be provided via BiPro Elite whey protein isolate.

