6.8 Outcome Variables

- VO₂peak Test
 - VO₂peak
 - Peak Power
- INT and TTE Protocol
 - Peak Power
 - Average Power
 - RPE
 - Total time to exhaustion at 90% VO₂peak
- Anthropometrics
 - Height
 - Weight
 - Age
 - Body Fat Percentage
- HRV
 - Root mean square of the successive differences of R–R intervals (RMSSD)
- Sweat Rate Determination
 - Individual sweat rate pre-post exercise

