17.0 Data Management* and Confidentiality

17.1 All statistical analyses will be conducted via the Statistical Package for Social Science (SPSS) software for Windows version 21 (SPSS Inc., Chicago, IL). Data will be statistically analyzed using separate 1-way analysis of covariance (ANCOVA) for TTE, HRV-Slope Recovery, and Sweat Rate measures. The pretest and

the posttest values will be used as a covariate and dependent variable, respectively. If the ANCOVA is significant, Fisher's LSD Post-Hoc analysis will be used to determine group differences. For effect size (ES), the partial eta squared statistic will be reported, with 0.01, 0.06, and 0.14 representing small, medium, and large ES, respectively. The significance level will be set at $p \leq 0.05$.

17.2 The calculation of sample size (G*Power 3.1.9.4) was based on pilot data in low-to-moderately trained young men (22.1 + 3.2 years) collected in our lab using the same protocol (90% PPO TTE) as outlined in this study. The total sample size was determined to be a total of 18 (6 in each group) based on a one-way ANCOVA, power of 0.90, and an alpha of 0.05. However, due to potential dropout rates, a total of 30 participants (10 per group) will be recruited with the goal of completing 18.

17.3 Individual results will remain confidential and only be related to the participant upon request once the study is completed. All questionnaires and data collection sheets will be kept in a locked cabinet during and following the study. Data that is electronically stored will be kept on a password-protected computer in the office of the investigator who oversees data collection. All information will be destroyed six years from the end of the study. Participant folders will be marked with an I.D. number to protect against a breach of confidentiality. Participant names and I.D. numbers will be stored apart from the subject folders in a password protected electronic file.

17.4 Quality control of collected data will be performed by ensuring all data files remain in filing cabinets when not in use.

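### The Primary Objective in 1.0 (no significant difference among the three drinks, placebo included) contradicts hypotheses 1 and 2 in 2.2 and, under the planned test, could be met only by a non-significant result

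*Combined protocol and SAP*

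**What the plan says.** The row labelled Primary Objective in 1.0 says the study is to demonstrate that "performance in a subsequent bout of high-intensity glycogen depleting exercise will not be significantly different regardless of post-exercise recovery drink". The parenthesis that follows lists all three drinks, placebo among them.

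Section 2.1 is neutral: it sets out to examine the effects of the drinks. Section 2.2 then gives three hypotheses:

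1. "Carbohydrate will improve subsequent performance significantly better than the placebo post-exercise in male Masters Class Athletes"
2. "Carbohydrate and protein will improve subsequent performance significantly better than PLA post-exercise in male Masters Class Athletes"
3. "Carbohydrate and Protein will not improve subsequent performance significantly better than CHO post-exercise in male Masters Class Athletes"

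Section 5.0 describes drinks "matched for taste and appearance between exercise bouts to elucidate which drink moderates" performance decrements most effectively. That is an exploratory aim and fits a test of difference.

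On analysis, 17.1 states: "Data will be statistically analyzed using separate 1-way analysis of covariance (ANCOVA) for TTE, HRV-Slope Recovery, and Sweat Rate measures". The pretest value is the covariate, and Fisher's LSD comparisons follow only if the ANCOVA is significant. Section 17.2 sizes a one-way ANCOVA at 90% power and alpha 0.05, giving 18 completers (6 per group) from 30 recruited.

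No section ties performance to one primary outcome. Study Endpoints (4.0) says only when the study ends: "The study will be completed when participants have finished all visits to the laboratory". Section 6.8 lists peak power, average power, RPE and TTE without ranking them. Section 17.1 analyses TTE, HRV slope and sweat rate without calling any of them primary.

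**The concern.** Sections 1.0 and 2.2 ask for opposite verdicts on the same two comparisons, CHO against placebo and CHO-P against placebo. A null trial would meet the stated Primary Objective, and a positive trial could meet the hypotheses, so either result could be reported as confirmation.

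The objective in 1.0 also rewards a weak trial. Under a test of difference, the only result that agrees with it is non-significance. If a true effect exists, non-significance becomes more likely as the trial gets smaller. This applies to 1.0, and to hypothesis 3 taken alone. It does not apply to 2.2 as a set, because hypotheses 1 and 2 require significance.

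**Working it through.** **The wording, comparison by comparison**

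| Comparison | 1.0 | 2.2 |
|---|---|---|
| CHO vs PLA | no significant difference | CHO significantly better |
| CHO-P vs PLA | no significant difference | CHO-P significantly better |
| CHO-P vs CHO | no significant difference | CHO-P not significantly better |

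The first two rows conflict; only the third agrees. Sections 17.1 and 17.2 test for, and size for, a difference, so they side with 2.2. Section 1.0 is the outlier.

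**What effect the plan's 18 implies**

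The documents give no planning effect or SD, so 18 cannot be reproduced forwards and has to be solved backwards.
- Omnibus F with 3 groups and 1 covariate: df1 = 2, df2 = N − 4 = 14, noncentrality N·f².
- Power 0.90 at N = 18 gives f = 0.938. At N = 15 it would need f = 1.06. With equal groups, any f from about 0.94 to 1.06 therefore returns 18.
- If both active drinks exceed placebo by d adjusted SD (SD after adjustment for the covariate), f = d·√2/3. Then d = 0.938 × 3/√2 = 1.99, and the upper end is 1.06 × 3/√2 = 2.25.

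The sizing thus aims to detect a very large difference, while 1.0 aims to show none.

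**How often each statement would be met**

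The effect sizes are assumptions. I simulated the 17.1 ANCOVA with a random baseline covariate, alpha 0.05 and LSD only after a significant omnibus test, using 60,000 trials per cell. Both active drinks exceed placebo by the same amount. 1.0 counts as met when the omnibus test is not significant. 2.2 counts as met when both active drinks are significantly above placebo and CHO-P is not significantly above CHO.

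| True effect (adjusted SD) | 6 per group: 1.0 / all of 2.2 / neither | 10 per group: 1.0 / all of 2.2 / neither |
|---|---|---|
| 0 | 95% / 0.4% / 5% | 95% / 0.4% / 5% |
| 0.8 | 78% / 11% / 11% | 61% / 23% / 16% |
| 1.2 | 55% / 30% / 15% | 27% / 56% / 17% |
| 1.99 | 12% / 77% / 11% | 0.7% / 95% / 4% |

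No trial can meet both, by definition. The 12% exceeds the formula's 10% because chance covariate imbalance costs a little power.

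The protocol's own benchmarks for partial eta squared (η²) give a second view, by formula with f² = η²/(1 − η²). The chance of a non-significant omnibus test at N = 18 is 94% (0.01), 87% (0.06) and 74% (0.14, the protocol's large effect). At N = 30 it is 93%, 80% and 55%.

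**Hypothesis 3**

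The confidence-interval half-width for CHO-P minus CHO is t·√(2/n) adjusted SD, with df = 3n − 4.
- n = 6 (df 14): 90% CI 1.761 × 0.577 = 1.02; 95% CI 2.145 × 0.577 = 1.24.
- n = 10 (df 26): 90% CI 1.706 × 0.447 = 0.76; 95% CI 2.056 × 0.447 = 0.92.

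These ignore covariate imbalance and are slightly optimistic; the simulated 95% figure at n = 6 is 1.26.

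**If a no-difference aim were kept**

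This uses two one-sided tests, true difference 0, alpha 0.05 per side and 90% power, with assumed margins of 1.0 or 0.8 adjusted SD. The normal approximation for one pair is n = 2·((1.645 + 1.645)/margin)², which gives 22 or 34 per group. With the t distribution it is 23 or 35. For all three pairs to pass, it is 28 or 44.

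**The case against.** The strongest reply is that this is one sentence in a summary table. Sections 2.2, 17.1 and 17.2 agree with each other, and nothing in allocation, data collection, model or sample size depends on 1.0. Harm arises only if someone judges the trial by 1.0 and ignores 2.2. That is true about cost. However, 1.0 is the one statement labelled Primary Objective, so it is a natural yardstick for the result.

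The authors may have meant the no-difference wording for CHO-P against CHO only. That is possible, but the parenthesis names placebo, so the text needs correcting under that reading too.

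The reading may seem uneven, since hypothesis 3 uses similar language and is treated more gently. The difference is that 1.0 claims to demonstrate the absence of a difference, whereas hypothesis 3 predicts a test result. The documents do not say that p > 0.05 will be read as equivalence. Hypothesis 3 is accordingly a lower-priority point.

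TTE can be identified by elimination: it is the only performance measure that 17.1 tests, and the 17.2 pilot used it. This stands as a reason to propose TTE, but it does not replace a stated primary outcome.

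The simulation rests on assumed effects and one pattern of means. That also stands. With PLA, CHO and CHO-P at 0, 0.6 and 1.2 SD and 6 per group, the shares are about 65% / 11% / 24%. At 2.25 SD, the upper end of the range that returns N = 18, 1.0 is met in about 6% of trials rather than 12%. The figures illustrate the stakes; the contradiction does not rest on them.

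**Conclusion.** The point holds and should be fixed; confidence is high. As written, 1.0 cannot be true together with hypotheses 1 and 2, and the planned analysis cannot establish it. That conclusion follows from the wording alone.

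The size of the risk depends on assumed effects. With equal active drinks and 6 completers per group, the objective in 1.0 would be met in about 78% of trials at a true effect of 0.8 adjusted SD and 55% at 1.2, although the drinks differ from placebo. At about 2.0 SD, the smallest effect for which 18 gives 90% power under this pattern, the share falls to 12%.

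This is not a finding that 18 is wrong. The documents give no planning effect against which to check it.

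**What to change.** 1. **Must fix.** Restate the Primary Objective in 1.0 to match 2.2: superiority of CHO over placebo and of CHO-P over placebo on baseline-adjusted second-bout performance. Name the outcome in 1.0 and in Study Endpoints (4.0). TTE is the natural choice, but the protocol names no primary, so the investigator should confirm it.
2. **Lower priority, hypothesis 3 only.** Always report the ANCOVA-adjusted CHO-P minus CHO difference with its 95% CI, whether or not the omnibus test is significant. State that p > 0.05 will not be read as equivalence.
3. **Only if a no-difference aim is kept.** Fix a margin before unblinding, specify the matching test or confidence-interval rule, and re-derive the sample size.

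Items 1 and 2 cost a reworded objective, one named outcome and one extra line of output. The 17.1 test is unchanged, and this point does not require a change to the sample size. The price is candour about hypothesis 3: with a 90% CI half-width of about 1.0 adjusted SD at 6 per group, CHO-P against CHO will probably be reported as inconclusive.

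Item 3 is expensive. Under the assumptions above it needs about 23 to 35 completers per group for one pair, or 28 to 44 for all three, against the 6 in 17.2.

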2.0 Objectives*

- 2.1 The purpose of this investigation is to examine the effects of carbohydrate vs. carbohydrate-protein co-ingestion vs. placebo on a subsequent bout of performance following high-intensity exercise and a 2-hour recovery period in Masters Class Athletes.
- 2.2 It is hypothesized that:
 - Carbohydrate will improve subsequent performance significantly better than the placebo post-exercise in male Masters Class Athletes.
 - Carbohydrate and protein will improve subsequent performance significantly better than PLA post-exercise in male Masters Class Athletes.
 - Carbohydrate and Protein will not improve subsequent performance significantly better than CHO post-exercise in male Masters Class Athletes.

3.0 Background*

- 3.1 The rate of participation by masters class athletes (MCA's) in organized endurance and ultra-endurance (>6 hours) events has increased exponentially over the past 10-15 years (Lepers et al. 2013; Lepers and Stapley 2016). MCA's are generally classified as ≥ 35 years of age who meticulously train for and compete in organized sport (Ransdell et al., 2009; Lepers and Cattagni 2012; Lepers and Stapley 2016; Fien et al. 2017). Carbohydrate and protein are key nutritional factors that promote glycogen and protein synthesis, support recovery and allow for repetitive high-intensity efforts. Few studies, however, have examined short-term (2-6 hours) post-exercise recovery nutrition specific to MCA's (Doering et al. 2016a, 2017).

MCA's (cyclists) maintain weekly mileage of approximately 250 – 350 miles per week, with no significant difference between younger (35-44 years) and older (≥ 55) age groups. Endurance exercise at this level of competition requires prolonged high-intensity activity of $\sim 70\text{-}90\%$ $\text{VO}_{2\text{max}}$, which relies quite heavily on carbohydrate oxidation (Romijn et al. 1993; Spriet 2007). Competitive athletes rely on their ability to both store and mobilize glucose from muscle. The storage form of glucose in muscle is glycogen. Typical glycogen depleting protocols in studies that have examined the difference between carbohydrate (CHO) ingestion or carbohydrate-protein (CHO-P) co-ingestion have been running

or cycling to fatigue at 70% VO₂max or intermittent exercise at 70%-90% VO₂max. These protocols have been sufficient for depleting muscle glycogen content to ~100 – 200 mmol/kg/dw (Tsintzas et al. 1995; Jentjens et al. 2001; Alghannam et al. 2016; Dahl et al. 2020). Conversely, both CHO (1.2 g/kg) and CHO-P co-ingestion (0.8/0.4 g/kg) were found to be equally effective for promoting glycogen resynthesis during varying periods of acute recovery (3, 4, and 5 hours) (van Loon et al. 2000; Jentjens et al. 2001; Alghannam et al. 2016; Dahl et al. 2020).

Consuming carbohydrates immediately post-exercise has been shown to increase glycogen resynthesis rate by three times as compared to delaying carbohydrates for 2-hours (Ivy et al. 1988). Ivy et al. (1988) demonstrated the rate of glycogen synthesis to be 45% slower when delaying carbohydrate intake by 2 hours. Consequently, muscle glycogen concentration was also significantly less when carbohydrate intake was delayed by 2 hours following high-intensity intermittent exercise (Ivy et al. 1988). A similar pattern was shown for leg protein synthesis when a CHO-P supplement (10 g protein; 8 g carbohydrate; 3 g fat) was provided immediately post-exercise in comparison to 3 hours later (Levenhagen et al. 2001).

Two different isoenergetic options have been shown to effectively promote glycogen resynthesis post-exercise: CHO only (1.2 g/kg) or CHO-P co-ingestion (0.8 g/kg/0.4 g/kg). Several studies had demonstrated an equivalent increase in muscle glycogen content (van Loon et al. 2000; Jentjens et al. 2001; Alghannam et al. 2016) when these recovery beverages were consumed beginning immediately post-exercise and at 30-min intervals after that for 3, 4, and 5-hour recovery periods, or an increase in favor of CHO-P co-ingestion when consumed immediately-post and at 1-hour intervals during the first 2 hours (Berardi et al. 2006).

MCA's may train twice per day, with limited time between bouts of exercise; therefore, an effective recovery strategy is paramount. On two occasions, CHO-P co-ingestion has been associated with either increased performance or an attenuated decrement to performance during a subsequent bout of endurance exercise in younger athletes (Berardi et al. 2008; Dahl et al. 2020). Appropriate post-exercise nutrient intake is vital for MCA's as several studies have reported slower recovery from muscle-damaging exercise, even when moderate amounts of protein are consumed (Doering et al. 2016a, 2017).

Post-exercise nutrient intake in a group of Australian (endurance) MCA's was reported to be well below the suggested amount for CHO (~0.7 g/kg) and slightly below the recommended threshold for protein (~0.3 g/kg) (Doering et al. 2016b). Furthermore, the MCA's surveyed in this study demonstrated poor or no knowledge of post-exercise nutritional practices for CHO and protein intake (Doering et al. 2016b). It has been suggested that while endurance athletes are familiar with the need for carbohydrates in the diet, the importance of meeting total daily protein needs as well as the incorporation of protein within the immediate-post recovery period may be less well understood (Vitale and Getzin 2019). Inadequate nutrient intake in the acute post-exercise recovery period may compromise the rate of both glycogen and protein synthesis. On a cellular level, this may negatively affect skeletal muscle remodeling and glycogen storage, promoting fatigue and poor training outcomes and performance (Ivy et al. 1988; Breen et al. 2011; Kruseman et al. 2020).

In conclusion, the rate of MCA participation in elite-level endurance competition is exponentially increasing. In contrast, the level of nutritional knowledge and recovery practices was reportedly poor in one group of surveyed endurance MCA's (endurance) athletes. Additionally, a critical gap in post-exercise recovery research exists specific to MCA's. Even less research exists specific to the MCA and short-term (2 hours or less) recovery. This is a problem as slower recovery rates between subsequent bouts of exercise have been demonstrated, and higher protein needs post-exercise have been indicated to promote muscle remodeling. A unique opportunity exists to examine CHO-P co-ingestion in a 2-hour recovery period to promote optimization of post-exercise glycogen resynthesis and protein remodeling to support successive bouts of training or competition.

4.0 Study Endpoints*

- 4.1 The study will be completed when participants have finished all visits to the laboratory. It is anticipated that the total testing for each individual should be completed within 14 days or 3-4 total visits.

5.0 Study Intervention/Investigational Agent

- 1.1 Participants will consume either a CHO beverage (1.2 g/kg of bw), a CHO-P beverage (0.8 g/kg bw CHO + 0.4 g/kg bw protein), or PLA beverage matched for taste and appearance between exercise bouts to elucidate which drink moderates

performance decrements most effectively. The dietary source of CHO will be Gatorade®, the PLA will be Gatorade® G Zero, and the protein will be provided via BiPro Elite whey protein isolate.

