6.0 Procedures Involved*

6.1 To test the hypothesis, this study will utilize a randomized, double-blind, placebo-controlled between-subject design to examine the effects of CHO and CHO-P supplementation on short-term recovery following aerobic interval exercise and time to exhaustion testing in MCA's. After completing the informed consent and screening process (Visit #1), each participant will be assessed for their anthropometric measures as well as body composition and will complete a GXT to volitional exhaustion on a cycle ergometer to determine VO₂peak. Participants will also be provided with the option to return to the lab on a separate date for the GXT and VO₂peak testing. Forty-eight to 72 hours after Visit #1, or VO₂peak testing, participants will return to the lab for familiarization with the INT exercise protocol and TTE (Visit #2). Within five to nine days after familiarization (Visit #2), participants will return to the lab for Visit #3 to complete INT exercise and TTE, a 2-hour passive recovery period including the consumption of one of three treatments (CHO, CHO-P, PLA), followed by repeated INT exercise and TTE, HRV and SR determination. Participants will also complete the Nutritional Recovery Practices, Knowledge, and Beliefs of Australian Triathletes survey during the 2-hour recovery period. Participants will be asked to complete the ASA24®, an automated self-administered 24-hour dietary assessment tool during the 5-9-day period between familiarization (Visit #2) and the experimental protocol (Visit #3).

Testing Procedures.

- Participants will report to the testing location on 3 separate occasions.
- Visit #1: The study will be explained to the participant by the investigators. Participants will be asked to provide their written, informed consent. The participants will then be asked to complete the American College of Sports Medicine Exercise Preparticipation Health Screening Questionnaire for Exercise Professionals (PHSQEP), Physical Activity Readiness Questionnaire for Everyone (PAR-Q+), and Medical Health and Activity Questionnaire.

Following the written consent and screening process, anthropometrics and body composition will be measured, and the VO₂peak test outlined in section 6.3 will be completed. Following informed consent, screening, and anthropometrics and body composition, if necessary (i.e., due to time constraints), participants may choose to return to the lab on a separate occasion for VO₂peak testing.

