- Visit #2: Participants will report to the testing location for familiarization to the testing protocols. Based on VO₂peak data obtained during Visit #1, participants will perform the INT and TTE protocol outlined in section 6.4 to familiarize them with the protocol for the experimental trial (Visit #3), and teach them how to respond to the rating of perceived exertion RPE measures.
- Visit #3: To ensure participants are hydrated prior to the start of testing, they will be asked to consume 500 ml of water 2 hours before their arrival to the laboratory for testing (Moreno et al. 2013; Vanderlei et al. 2015). Participants will complete a warm-up followed by the INT and TTE protocol, as outlined in section 6.4. Immediately following the INT and TTE testing, the participant will be given an isocaloric CHO (1.2 g/kg of bw), CHO-P (0.8 g/kg bw CHO + 0.4 g/kg bw protein), or PLA beverage that have a similar appearance and taste and will be blinded to the contents. Participants will rest for two hours and then repeat the INT and TTE testing (6.4). Participants will be weighed in their cycling bib shorts immediately before and after the first and second bouts of INT exercise and TTE testing. Sweat rate will be determined based on the difference between pre-and post-weight changes for each bout of exercise, the amount of fluid consumed during the recovery period, and total exercise time in minutes (Casa 2019). Participants will also be asked to report total sleep in number of hours and minutes for the night prior to testing. Immediately upon completion of the second exercise bout, participants will rest for an additional 30 minutes for HRV recording. Completion of Visit #3 will conclude all required testing.

6.2 Anthropometric measurements:

- Participants will be assessed for body weight, height, and body composition.

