10.0 Inclusion and Exclusion Criteria*

10.1 Individuals will be screened for eligibility using the American College of Sports Medicine Exercise Preparticipation Health Screening Questionnaire for Exercise Professionals (PHSQEP), Physical Activity Readiness Questionnaire for Everyone (PAR-Q+), and confidential Medical Health and Activity Questionnaire to determine the need for medical clearance from a health care professional. Participants presenting

any sign or symptoms suggestive of cardiovascular, metabolic, or renal disease will be asked to seek medical clearance in order to participate.

10.2 Inclusion Criteria.

- Men between the ages of 35 and 59 years
- Free of any physical limitations as determined by the Exercise Preparticipation Health Screening Questionnaire for Exercise Professionals (PHSQEP), and a Physical Activity Readiness Questionnaire for Everyone (PAR-Q+)
- Regularly engaged in endurance exercise (running, cycling, swimming) for a minimum of three years, a weekly training volume of 5-10 hours, and a maximal oxygen uptake of $45.00 \text{ ml}\cdot\text{kg}^{-1}\cdot\text{min}^{-1}$ or higher as determined by completion of $\text{VO}_{2\text{peak}}$ assessment (Visit #1).

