10.3 Exclusion Criteria

- Recent musculoskeletal injuries or surgeries
- Any chronic illness that requires continuous medical care
- Current incarceration, cognitive impairment or inability to provide consent
- Present or past use of performance-enhancing drugs

10.4 Indicate specifically whether you will include or exclude each of the following special populations:

- Adults unable to consent: exclude
- Individuals who are not yet adults (infants, children, teenagers): exclude
- Pregnant women: exclude
- Prisoners: exclude

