15.0 Risks to Subjects*

15.1 The exercise-based assessments carry the same inherent risks as participating in any physical activity, such as muscle soreness, and fatigue and possibly muscle strains, and/or joint sprains, elevated heart rate, feelings of nausea and possible episodes of emesis, arrhythmia, myocardial infarction, and death. To minimize these risks, participants will be instructed on the appropriate technique for the performance assessments and will be required to complete a warm-up prior to completing the assessments. Furthermore, participants will be informed that they can quit at any time before or during the test. All personnel involved in this study are CPR certified. Furthermore, all research personnel involved in data collection are experienced in the administration of the proposed assessments, and all Doctoral students involved in this study are Certified Strength and Conditioning Specialists through the National Strength and Conditioning Association. Participants will be instructed to immediately stop and report any injury or discomfort associated with the performance assessments to a member of the investigative team. The extent of the injury/discomfort, as well as the ability of the participant to continue with the study, will be subsequently be determined by the investigative team. If it is deemed that the discomfort/injury will prevent the participant from completing the study, or if the injury/discomfort may be exacerbated by further participation in the study, the investigative team will suspend the individual's participation in the study.

15.2 This study is recruiting for male participants only. Therefore, subjects who are pregnant will not be enrolled.

15.3 There are no risks to others in the study who are not participants.

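### One of the three masked drinks contains whey protein, but no eligibility criterion names allergy or intolerance to a drink ingredient, and the risk section lists no drink-related risk

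*Combined protocol and SAP*

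**What the plan says.** The intervention is one of three drinks: carbohydrate, carbohydrate plus protein, or placebo. For the second of these, Section 5.0 says that "the protein will be provided via BiPro Elite whey protein isolate", at 0.4 g/kg of body weight. Section 6.1 describes a "randomized, double-blind, placebo-controlled between-subject design". Its account of Visit #3 has the drink given immediately after the first exercise bout and refers to a "PLA beverage that have a similar appearance and taste and will be blinded to the contents".

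Eligibility is set in Section 10. The inclusion list (10.2) covers sex and age, physical limitations judged by two exercise-readiness questionnaires, training history and oxygen uptake. The exclusion list (10.3) has four entries: recent musculoskeletal injury or surgery; "Any chronic illness that requires continuous medical care"; incarceration, cognitive impairment or inability to consent; and past or present use of performance-enhancing drugs. Section 10.1 uses the questionnaires, including a Medical Health and Activity Questionnaire, to decide who needs medical clearance, and names cardiovascular, metabolic or renal signs or symptoms as the trigger.

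Section 15.1 opens with "The exercise-based assessments carry the same inherent risks as participating in any physical activity" and goes on to list the hazards of exertion. The rest of Section 15 deals with pregnancy and with risks to non-participants.

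**The concern.** Whey is a milk protein. In a trial that feeds it to one group under masking, a reader expects the eligibility list to ask about allergy or intolerance to what is in the drinks, and the risk list to mention the drinks. Neither does. A man who manages a milk allergy by avoiding milk loses his usual means of avoidance once the drink is masked. If the staff who hand it over are masked too, as the double-blind label implies, they cannot intercept it either. The drink comes straight after exercise to exhaustion, and the same exercise is repeated two hours later. What is at stake is a foreseeable and preventable reaction in a volunteer who is promised no direct benefit (Section 16.1).

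**Working it through.** The documents state no figure to reproduce. The check sets the intervention, eligibility, risk and safety sections side by side and asks whether any written rule stops a man with known milk-protein allergy before he is given the drink.

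1. **Does an inclusion criterion stop him?** No. Section 10.2 concerns sex, age, physical limitation, training and oxygen uptake. A fit endurance athlete with a food allergy can meet all of them.
2. **Does an exclusion criterion stop him?** Not clearly. The nearest is "Any chronic illness that requires continuous medical care". An allergy or intolerance handled by avoidance need not require continuous care, so this entry cannot be relied on to cover him.
3. **Does the screening rule stop him?** Not as written. The Medical Health and Activity Questionnaire may ask about allergies; its content is not reproduced. But the use stated for it in 10.1 is to decide on medical clearance, and the only trigger named is cardiovascular, metabolic or renal signs. No written rule acts on an allergy answer.
4. **Does the risk section mention the drinks?** No. Section 15.1 is about the exercise tests. It includes nausea and emesis, but as effects of exercise.
5. **Does safety reporting cover a reaction to the drink?** Partly. The stop-and-report instructions in 15.1 and 18.1 are tied to the performance assessments, whereas the drink is taken at the start of a rest period. Section 20.1 is broader: participants report any discomfort related to the study, the emergency medical system is used if immediate help is needed, and adverse events go to the IRB. All of this acts after exposure.

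**Number exposed.** Section 17.2 plans "a total of 30 participants (10 per group) will be recruited with the goal of completing 18". That gives 10/30 = 33% assigned to whey. Section 12.2 instead caps enrolment at 50. If the three groups were equal and everyone enrolled were dosed, 50/3 = 16.7, so about 17 men. This is an upper bound, because enrolment under 12.2 comes before the oxygen-uptake threshold is applied and before any dropout.

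**Amount.** Body weight is not given. Assuming 60 to 100 kg, 0.4 × 60 = 24 g and 0.4 × 100 = 40 g of whey protein.

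**The case against.** The strongest reply is that a known milk allergy would probably surface anyway. The study is explained and written consent is taken before screening (6.1). An investigator is available for questions (22.0). A participant may stop without penalty, and the researchers may end his participation at any time (14.1). The consent pages and the questionnaire were not available for review, and either may disclose the whey or ask about allergy. Much of this stands. Masking hides which drink a man gets; nothing in the documents says it hides that whey is a possible ingredient. A reader might infer that an allergic man cannot avoid the exposure, and the documents do not support that. What remains is that consent and the right to withdraw leave it to the man to make the connection, and the investigators have discretion but no written criterion to apply.

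A reader might also infer a bias: reactions confined to the whey arm would shorten the second time to exhaustion there and count against the carbohydrate-protein hypotheses in 2.2. That goes too far, for three reasons.

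- Whey is not the only thing that differs between arms. Carbohydrate is 1.2 g/kg, 0.8 g/kg or a G Zero placebo, so gut symptoms from a drink need not be confined to one arm. Only milk-specific reactions would be.
- Under 14.3 a man who withdraws has his data removed, so he would not be among the planned six completers per group (18/3).
- The expected number is small on any plausible input. Purely as an illustration, if 0.5% to 2% of volunteers were affected (an assumption, not in the documents), six completers would include 6 × 0.005 = 0.03 to 6 × 0.02 = 0.12 affected men.

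A probability that at least one allergic man is given whey could be computed in the same way. It would rest on that same outside prevalence and on nobody declining, so none is claimed.

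**Conclusion.** The gap in the text is real. Followed as written, Section 10 admits a man with known milk-protein allergy to a trial in which about one participant in three is given masked whey, and Section 15 does not tell the reader that the drinks carry any risk. The conclusion rests on two readings: that a food allergy is not ordinarily an illness needing continuous care, and that no unseen document adds an exclusion to those in 10.2 and 10.3. It makes no claim about what the consent form says.

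This is a cheap improvement to participant safety. It does not undermine a hypothesis, the sample size or the ANCOVA, and it does not by itself stand in the way of the trial.

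**What to change.** Bring Sections 10 and 15 into line with the ingredients named in 5.0:

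- Add to 10.3 an exclusion for known allergy or intolerance to milk or whey protein, or to any other ingredient of the study drinks.
- Check it at Visit #1, before randomization, using the Medical Health and Activity Questionnaire already completed there. If that form does not ask about allergy, add one question. The drink is not given until Visit #3, so the check fits the existing schedule.
- Add allergic and gastrointestinal reactions to the drinks to the risks in 15.1.

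The cost is one exclusion line, at most one screening question and one risk sentence. The only downside is losing an occasional volunteer who would otherwise qualify. The drinks, visits, sample size and analysis stay as they are.
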